5. The patient has given signed informed consent.
6. TAVI performed via the femoral artery.

Centers eligible for inclusion: Scandinavian and European centers who fulfill the above mentioned criteria.

Randomization:

Before randomizing patients, the center decides which two valves the patient is found eligible for, and enters these valves in the electronic randomization form (TrialPartner). Randomization is then performed between these two valves. A patient is only randomized if a dedicated technical TAVI conference has found the patient eligible for treatment with both valves.

Consecutive cohorts are established.

We plan to initiate the following cohorts:

Cohort A: Patients randomized to the Sapien or the Accurate neo 2 TAVI valve (Approved, not recruiting, await funding).

Cohort B: Patients randomized to the Sapien or the Myval TAVI valve (Recruiting).

Cohort C: Patients randomized to a BEV valve (To be determined whether Sapien or Myval) compared to the Navitor valve (Awaits approval and funding).

Operator requirements:

Any procedure requires that the physician has performed at least 15 implantations with the valve in use. Otherwise the procedure is performed according to the routine of the institution.

Primary endpoints, for each cohort:

1. MACE: Mortality, stroke, moderate/major PVL, moderate/severe valve deterioration at 1 year, using VARC-3 criteria (10).

Secondary endpoints, for each cohort:

1. MACE: Mortality, stroke, moderate/major PVL, moderate/severe valve deterioration at 30-day, 3-year, 5-year and 10-year, using VARC-3 criteria (10).
2. Mortality: 30-day, 1-year, 3-year, 5-year and 10-year.
3. Stroke: During admission, 30-day, 1-year, 3-year, 5-year and 10-year, using VARC-3 criteria (10).
4. Moderate or severe PVL: 30-day, 1-year, 3-year, 5-year and 10-year, using VARC-3 criteria (10).
5. Moderate or major valve deterioration: 30-day, 1-year, 3-year, 5-year and 10-year, using VARC-3 criteria (10).
6. Pacemaker-implantation: during admission, 30-day, 1-year, 3-year, 5-year and 10-year.
7. Major bleeding resulting in drop in hgb-level ≥ 1.86 mmol/l and/or erythrocyte transfusion ≥ 2 units: during admission, 30-day, 1-year, 3-year, 5-year and 10-year, modified from BARC type 3-5 criteria (11, 12).
8. 6-minute walk test: baseline, 30-day, 1-year, 3-year, 5-year and 10-year.

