Table: Various event-rates, non-inferiority margins and sample sizes estimated for non-inferiority studies with and without drop-out, and with and without interim analyses. Power=0.80. Alfa=0.05.

Event rate	Non-inferiority margin	Relative non-inferiority margin	No drop-out, No interim-analysis	No drop-out, 2 interim-analyses	5% drop-out, no interim-analyses	5% drop-out, 2 interim-analyses
Closest non-inferiority margin (1.decimal) if no. of included patients is 1062, without interim-analyses and with 5% drop-out (As planned in cohort B)						
7	≈4.0	0.57				
9	≈4.5	0.50	1009	1017	1062	1071
11	≈5.0	0.45				
13	≈5.3	0.41				
Closest non-inferiority margin (1.decimal) if no. of included patients is 1345, With interim analyses and 5% drop-out (As planned in cohort A)						
7	≈3.6	0.52				
9	≈4.0	0.44	1268	1279	1336	1346
11	≈4.4	0.40				
13	≈4.7	0.36				
Study size if fixed non-inferiority margin = 4%						
7	4	0.57	1008	1017	1062	1070
9		0.44	1268	1279	1335	1346
11		0.36	1514	1527	1594	1607
13		0.31	1750	1764	1843	1857
Study size if fixed non-inferiority margin = 4.5 %						
7	4.5	0.64	796	803	838	845
9		0.50	1002	1011	1055	1064
11		0.41	1198	1208	1262	1272
13		0.35	1382	1394	1455	1467

For the MRI-substudy evaluating the hemodynamics (EOA, aortic regurgitation fraction), the expected EOA is 1.5 (SD 0.54) cm², and the expected regurgitation fraction 0.14 (SD expected to be 0.09). A total of 148 patients are needed to document a difference of 0.25 cm² in EOA (1.5 to 1.25 cm²) and 102 patients to document a difference of 0.05 in expected regurgitation fraction (0.14 to 0.09). The initial plan was to include 166 patients with an expected drop-out of 10% of patients. After inclusion of the first 166 patients in the MRI-substudy, inclusion was on hold for 1 year, and Myval was replaced by Myval Octacor. It was therefore decided to include another cohort in the MRI-substudy, comparing Sapien with Myval Octacor. To account

for higher than expected drop-out, the ethical committee was applied and approved that the MRI-substudy cohort was increased up to 360 patients. A HCT-substudy is performed with expected 850 patients evaluating occurrence of HALT at 1-month and 1-year. This substudy is descriptive.

Criteria used to perform interim analysis before planned or terminate the study before planned:

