For each cohort the maximal inclusion period is 3 years, and the first interim analysis (if planned according to the steering committee) will be performed after no later than two years of inclusion. A cohort will also be closed for inclusion, if one of the study valves is retracted from the market or replaced by a new generation of the device.

Number of centers and procedures per center: The prerequisite for initiating a comparison between two valves is that at least 3 centers will randomize from the beginning, that at least 10 centers are expected to randomize in each cohort, and that each center aims at including at least 50 patients per year.

Statistics: Data will be analyzed according to the intention-to-treat principle. Continuous data will be presented as mean \pm SD, and compared using a t-test, if data are normally distributed. If data are not normally distributed the Mann Whitney U test will be used. Categorical variables will be compared using Fischers exact test or Chi-square test as appropriate, and data presented as numbers and percentages. Significance level is $p<0.05$ (double sided). When comparing primary endpoints, a non-inferiority analysis will be used. When comparing secondary endpoints, Cox regression and logistic regression analyses will be used, as appropriate. Kaplan-Meir curves will be used for graphical presentation of time to events.

Data management: Data will be collected and stored according to the Danish data protection legislation. TrialPartner will be used for the Electronic Case Report form (ECRF). Patient and procedural characteristics will be entered in the ECRF following the procedure and at time of discharge. Follow-up (30-day, 1-year, 3-year, 5-year and 10-year) will be conducted mainly registry based (CPR-registry, National patient registry, Invasive registry), but at each follow-up the site will also check for events, and file them in the ECRF. This will ensure two sources for event-registration. Regarding moderate and severe PVL, moderate and severe aortic stenosis, and presence of thrombus or leaflet thickening, data will be entered by the Echo and HCT core labs. MRI findings will be entered by the MRI core lab. TrialPartner is approved by the Danish data regulative, and data entry and access will be logged. When a cohort is terminated, data will be merged and anonymized and a key stored with the CPR-number.

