Biobank: No biobank is collected.

Blinding: The study is not blinded.

Data from patient records: As part of the study data on previous disease (hypertension, diabetes, stroke, myocardial infarction, congestive heart failure), age, sex, Echocardiographic findings, HCT-findings will be collected from the patient records. These data will only be used for study purposes, and will be anonymized when the study is terminated. In situations where these data cannot be collected from registries, they will be retrieved from patient records. The purpose is to use these data in anonymous form when publishing the final results.

Data management and approvals: The Danish Data protection legislation will be followed. The study will be filed to the Danish Data protection agency and the local Ethical committee, and filed to www.clinicaltrial.gov before inclusion starts. In Denmark the national board of health will applied for data from the CPR-registry and the national patient registry. Data can be shared in anonymous form for research purposes.

Access to data: Data is stored in TrialPartner. All data is encrypted. Any access or attempt to access data will be logged. Investigator/Institution will allow monitoring or audit from the ethical committee or the data protection agency as well as the national board of health who will be given access to source data and patient records. Investigator is responsible for ensuring that any patient has been given written consent to access source data (patient record).

Safety committee:

A separate safety committee is established for each cohort. The members are physicians not implanting TAVI-valves.

Event committee:

A separate event committee is established to adjudicate selected endpoints (Stroke, AMI, endocarditis, readmission with CHF).

Steering committee:

For each cohort a steering committee is established with one representative from each of the centers randomizing patients in this cohort. The chair is the physician who from the beginning is responsible for this cohort.

Coordinating center:

The research department at Aarhus University Hospital will be the coordinating center, and responsible for establishing a digital CRF for the trial, and responsible for collecting data, monitoring, coordinating safety committee, event committee and steering committee meetings and publications.

Economy/Funding:

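### No baseline adjustment is stated for the primary non-inferiority comparison, so a small amount of precision from data already collected goes unused

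*Combined protocol and SAP*

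**What the plan says.** All references are to the combined protocol and SAP.

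- **Primary endpoint** (Primary endpoints): "MACE: Mortality, stroke, moderate/major PVL, moderate/severe valve deterioration at 1 year, using VARC-3 criteria (10").
- **Primary analysis** (Statistics): "When comparing primary endpoints, a non-inferiority analysis will be used". No estimator, interval method, covariate or stratification factor is given.
- **Regression** (Statistics) is named for other endpoints only, and without covariates: "When comparing secondary endpoints, Cox regression and logistic regression analyses will be used, as appropriate".
- **Baseline data** (Data from patient records): "data on previous disease (hypertension, diabetes, stroke, myocardial infarction, congestive heart failure), age, sex, Echocardiographic findings, HCT-findings will be collected".
- **Sample size** (table under Power calculations): "Power=0.80. Alfa=0.05". Cohort B is planned at 1062 patients with 5% drop-out and no interim analyses. The margin is 4.0 points at a 7% event rate or 4.5 points at 9%.
- **Randomization** is between the two valves chosen for the patient. No stratification is mentioned. At least 10 centers are expected per cohort.

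**The concern.** Non-inferiority will be decided by whether one confidence limit clears a fixed absolute margin, and the planned power is only 80%. Variables such as age, prior stroke and heart failure plausibly predict part of the composite. Using them in a standardized (marginal) risk difference leaves the estimand and the margin unchanged and, in large samples, gives an interval that is no wider and usually a little narrower. It also corrects for chance imbalance in the modelled variables. The plan collects these variables but gives them no stated role in the primary comparison.

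The silence also leaves a choice open. In an unblinded trial, covariates could be added or left out after results by arm are visible. Fixing one estimator and one list beforehand closes that choice.

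**Working it through.** **Step 1. Reproduce the plan's figure.** Inputs from the table: event rate p = 0.07, margin δ = 0.04, power 0.80, alpha 0.05. Assumed: 1:1 allocation (the ratio is not stated) and true difference 0.

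N = 2 × ceil[(z_α + z_0.80)² × 2p(1−p)/δ²]

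At one-sided 0.05: (1.645 + 0.842)² × 2 × 0.07 × 0.93 / 0.0016 = 503.1 per arm, so N = 1008. Then 1008/0.95 = 1061.1, so 1062. Both match the table. All eight fixed-margin entries without drop-out or interim analyses reproduce within 2 patients. The formula has no covariate term, so the plan credits no gain from baseline data.

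**Step 2. Unadjusted power.** Analysed n = 0.95 × 1062 = 1008.9.

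SE = √[4 × 0.07 × 0.93 / 1008.9] = 0.01607. Power = Φ(0.04/0.01607 − 1.645) = 80.1%.

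**Step 3. How much could baseline variables explain?** The documents do not say, so this is an assumption shown over a range. Take a logistic model with one normally distributed prognostic score of slope s. Let R² = Var(risk)/[p(1−p)]. Adjustment multiplies the variance of the risk difference by about (1 − R²). Equivalent extra patients = n × [1/(1−R²) − 1].

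| s | AUC | R² at 7% | Extra patients on 1008 | R² at 9% | Extra patients on 1009 |
|---|---|---|---|---|---|
| 0.50 | 0.64 | 1.7% | 18 | 2.1% | 22 |
| 0.75 | 0.70 | 4.0% | 42 | 4.9% | 52 |
| 1.00 | 0.75 | 7.3% | 80 | 8.6% | 95 |

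**Step 4. Effect on cohort B** (N = 1062, one-sided 0.05). Half-width = 1.645 × SE × √(1−R²), in percentage points.

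| R² | Power, 7% events, margin 4.0 | Half-width | Power, 9% events, margin 4.5 |
|---|---|---|---|
| 0 | 80.1% | 2.64 | 80.3% |
| 0.01 | 80.4% | 2.63 | 80.6% |
| 0.02 | 80.8% | 2.62 | 81.0% |
| 0.05 | 81.8% | 2.58 | 82.1% |
| 0.09 | 83.3% | 2.52 | 83.5% |

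The gain is about 0.3 to 3 power points. For R² of 0.02 to 0.05 the half-width shrinks by only about 0.03 to 0.07 points.

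**Step 5. How large a model can the data carry?** Expected events: 0.07 × 1008 ≈ 71, or 0.09 × 1009 ≈ 91.

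- *Long model:* intercept, valve, 9 center terms for 10 centers, age, sex, four histories and 2 terms for three calcium levels make 19 coefficients, or 3.7 to 4.8 events per coefficient.
- *Short model:* intercept, valve, age, sex and four histories make 8 coefficients, or 8.9 to 11.4 events per coefficient.

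**Step 6. Check that the gain survives estimation.** Steps 3 and 4 treat the score as known, so they are a ceiling. Simulations that estimate the coefficients, with assumed covariate prevalences and weights, gave:

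- *Long model* (3000 trials per setting, Monte Carlo error up to about 1 point): nominal reductions of 2%, 5% and 9% at 9% events became about 0.3%, 2.7% and 7.0%. At least one center had no events in 33–35% of trials at 9% events and in about 50% at 7%. At 9% events the robust 90% interval covered 88.6–88.8%, against 89.3–89.9% unadjusted.
- *Short model* (N = 1008, 6000 trials per setting): variance fell by about 1–6% at 7% events and 2–10% at 9%. Coverage of the 90% interval stayed at 89.5–90.4%.

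**The case against.** The strongest reply is that nothing is wrong here. In a randomized trial the unadjusted risk difference is valid, matches the absolute margin and the sample-size method, and already meets the planned power. The plan also does not commit to an unadjusted test: it says nothing about the estimator, which is the more basic gap. Theoretical gains assume a perfectly known score, and a model with center terms would lose much of them and give slightly narrow intervals.

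Most of this stands. It limits the point to an optional gain in precision, and it rules out the long model. It does not remove the gain from the short model, which kept close to nominal coverage in simulation.

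A reader might infer more than the documents support:

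- *That strong predictors are being ignored.* No prognostic strength is given, and every AUC above is assumed. The composite also includes paravalvular leak and valve deterioration, which may depend on other variables, so the gain could sit at the low end.
- *That precision is critical because the margin is tight.* The plan's own table puts these margins at 0.44 to 0.57 of the event rate.
- *That adjustment is free and complete.* The documents do not say that the covariates will be complete for every patient, and adjustment addresses imbalance only in modelled variables.

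**Conclusion.** The point holds as a modest improvement. No adjustment is stated for the primary comparison, suitable variables are collected, and a standardized risk difference would use them on the same scale as the margin. The expected benefit is roughly a 1 to 9% reduction in variance, or about 0.3 to 3 power points in cohort B. This assumes a baseline AUC of about 0.64 to 0.75, 1:1 allocation, event rates of 7 to 9% and a short model. The advantage over the unadjusted estimate is guaranteed only in large samples.

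It would be wrong to conclude that the design misses its power target for want of adjustment. At one-sided 0.05 the target is met. A separate matter weighs far more: the Statistics section says "Significance level is $p<0.05$ (double sided"), while 1062 reproduces only at one-sided 0.05. At one-sided 0.025, power with 1062 patients is 70.2% and the required number is 1346 (1278/0.95 = 1345.3). Variance reductions of 2%, 5% and 9% would then give only 71.1%, 72.4% and 74.2%, so adjustment cannot stand in for resolving the alpha.

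**What to change.** In the Statistics section:

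1. Define the primary estimate as the difference in 1-year risk standardized over all randomized patients (g-computation) from a logistic model with valve, age, sex, prior stroke, heart failure, myocardial infarction and diabetes. Use a robust or bootstrap interval and compare its limit with the same absolute margin. Do not use a conditional odds ratio, which is not on the margin's scale.
2. Leave out individual center terms, or pool small centers by a stated rule.
3. Fix the covariate list and a simple rule for missing covariates before any data by arm are seen.
4. Report the unadjusted risk difference as a sensitivity analysis.

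The cost is a short paragraph, the missing-data rule and some programming. No new data, patients or change of margin are needed, and the sample size can stay as calculated, with any gain held as reserve.

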9. Other TAVI-related complications: conversion to open surgery during implantation, unplanned use of cardiopulmonary support (CPS), coronary artery obstruction, ventricular septal perforation, mitral valve apparatus damage or dysfunction, cardiac tamponade, valve embolization, valve migration, need for TAVI-in-TAVI deployment, using VARC-3 criteria (10).
10. Other TAVI-related complications: Annulus rupture, Aortic rupture.
11. Endocarditis, 30-day, 1-year, 3-year, 5-year, 10-year.
12. Proportion with successful implantation of the chosen valve. This means no need for more than 1 TAVI valve, no change to another valve than planned during the procedure because it was impossible to implant the valve planned, and no conversion to surgery or procedure-related death.
13. Major vascular access site and access-related complications resulting in endovascular or open surgery using VARC-3 criteria during admission and at day 30 (10).
14. Occurrence of valve thrombosis or severe stenosis (confirmed by TEE, TTE or CT), 30-day, 1-year, 3-year, 5-year and 10-year.
15. Readmission for congestive heart failure: 30-day, 1-year, 3-year, 5-year or 10-year.
16. Increase in renal creatinine level more than to $\geq 200\%$ (AKIN stage 2-3, VARC-3 criteria) or resulting in dialysis (AKIN stage 4) according to VARC-3 criteria: during admission and at day 30 (10).

17. Severity of PVL stratified according to level of annular calcium on CT (low/medium/high) at day 30.
18. Gradient (AO) stratified according to level of annular calcium on CT (low/medium/high) at day 30.
19. Prosthesis-patient mismatch (EOA/body surface area). Severe PPM \leq 0.65 cm²/m². Moderate PPM \leq 0.85 cm²/m², 30-day, 1-year, 3-year, 5-year and 10-year according to VARC-3 criteria (10).
20. Effective orifice area and volume of aortic regurgitation measured by MRI at 1 month (only patients included in MRI sub-study).
21. Leaflet thickening (hypoattenuated leaflet thickening = HALT) or reduced leaflet motion or thrombus assessed by HCT at 1 month and 12 month (only patients included in HCT sub-study).
22. Proportion with moderate or major commissural misalignment on 1 month HCT (only patients included in the HCT sub-study)
23. AMI, 30-day, 1-year, 3-year, 5-year and 10-year according to VARC-3 criteria (10).
24. PCI (not scheduled before TAVI), 30-day, 1-year, 3-year, 5-year and 10-year according to VARC-3 criteria (10).

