25. CABG (not scheduled before TAVI), 30-day, 1-year, 3-year, 5-year and 10-year according to VARC-3 criteria (10).
26. Reoperation (TAVR, SAVR, BAV), 30-day, 1-year, 3-year, 5-year and 10-year according to VARC-3 criteria (10).
27. Newly diagnosed atrial fibrillation/flutter, 30-day, 1-year, 3-year, 5-year and 10-year according to VARC-3 criteria (10).

Registration of endpoints:

The majority of endpoints are collected from national registries. An echo core-lab is established to evaluate echo parameters (degree of PVL moderate/severe, valve deterioration, thrombosis). A CT core-lab is established to evaluate CT parameters (leaflet thickening, reduced leaflet motion, leaflet thrombosis, coronary alignment). An MRI core lab is established to evaluate MRI parameters (EOA and volume of aortic regurgitation). A separate core lab is established for analysis of aortaograms (videodensitometry) following TAVI. Procedure-related complications are manually collected from electronic patient files. At each follow-up (1-month, 1-year, 3-year, 5-year, 10-year) each site also monitor events and file them in the ECRF, thus both site-reporting and registry-validation of events. Selected endpoints are adjudicated by an endpoint committee (Stroke, AMI, readmission with heart failure, endocarditis).

Power calculations:

For each cohort (randomized comparison between two valves) the steering committee decides to perform the study with or without interim analyses. In case interim analyses is chosen, a safety committee will compare outcome after inclusion of approximately 1/3 and 2/3 of patients (interim analyses). If one valve is

not clearly inferior, randomization will continue until the complete cohort is included. The size of the cohort is dependent of expected event-rate, chosen non-inferiority margin, number of interim analyses and expected drop-out. See table below. With 2 interim analyses and a non-inferiority margin of 4%, event rate 9% and expected drop out of 5% the sample size should be 1346 patients. If including 1062 patients as planned in cohort B, and with no interim analyses and 5% drop-out, the non-inferiority margin would be 4% if the event-rate is 7% and 4.5% if the event rate is 9%. If the observed event-rate differ significantly from the expected, the steering committee should consider adjusting sample size or non-inferiority margin (see table below).

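### Kaplan-Meier is the only planned time-to-event display and death is not treated as a competing event, so a 5- to 10-year curve for a non-fatal endpoint would overstate incidence

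*Combined protocol and SAP*

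**What the plan says.** The Statistics section is the only analysis text in the combined protocol and SAP. On display it says that "Kaplan-Meir curves will be used for graphical presentation of time to events", with no distinction between fatal and non-fatal endpoints. On comparison it says: "When comparing secondary endpoints, Cox regression and logistic regression analyses will be used, as appropriate". Categorical variables are to be tested by Fisher's exact or chi-square test, with "data presented as numbers and percentages".

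The list of secondary endpoints contains many non-fatal events followed to 10 years, among them:

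- "Reoperation (TAVR, SAVR, BAV), 30-day, 1-year, 3-year, 5-year and 10-year"
- "Endocarditis, 30-day, 1-year, 3-year, 5-year, 10-year"
- "Readmission for congestive heart failure: 30-day, 1-year, 3-year, 5-year or 10-year"
- "Pacemaker-implantation: during admission, 30-day, 1-year, 3-year, 5-year and 10-year"

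Death is collected over the same period as its own endpoint: "Mortality: 30-day, 1-year, 3-year, 5-year and 10-year". The Publications section plans a separate paper for each follow-up time, including 3, 5 and 10 years. The Background gives long-term monitoring of valve performance as a purpose of the organization.

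Nowhere does the document mention competing risks, cumulative incidence functions, cause-specific hazards or the treatment of death when the endpoint is non-fatal.

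**The concern.** Kaplan-Meier for a non-fatal event ordinarily censors patients when they die. Its complement (1-KM) then estimates what would be seen if the dead had gone on to have the event at the survivors' rate. A patient who has died cannot be reoperated or develop endocarditis, so 1-KM is higher than the share of implanted patients who have the event. The gap widens as deaths accumulate.

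At 1 year this hardly matters. At 10 years in a TAVI population it may. A reader who took 10-year reoperation or endocarditis from a curve would get a higher figure than the crude percentage in the same paper, and the plan offers nothing to explain the difference. Since some secondary endpoints are to be analysed by Cox regression, and Kaplan-Meier is the only curve named, it is likely that at least some non-fatal endpoints would be drawn this way.

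**Working it through.** **Inputs.** The documents state no figure that depends on this point, so there is none to reproduce. They give no 5- or 10-year mortality and no long-term rate for any non-fatal endpoint, and the composite event rates in the sample-size table do not fix one. The following are therefore assumptions:

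- M, 10-year mortality: 30% to 60%.
- K, 10-year 1-KM for the non-fatal event: 20%, with 5% and 30% as checks.
- a and b, Weibull shapes for event and death: 1 is a constant hazard, below 1 is early clustering, above 1 is a rising hazard.

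The one input from the documents is the planned cohort B size of 1062, which with equal arms (assumed) is 531 per arm.

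**Formulas.** Cumulative hazards are He(t) = -ln(1-K)·(t/10)^a and Hd(t) = -ln(1-M)·(t/10)^b. Then 1-KM(t) = 1 - exp(-He(t)), and the true cumulative incidence CIF(t) is the integral from 0 to t of exp(-He-Hd) dHe. With a = b = 1 this reduces to CIF(t) = He/(He+Hd) × [1 - exp(-(He+Hd))]. The overstatement factor is 1-KM divided by CIF.

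**Worked case, 10 years, constant hazards, K = 20%.** He = -ln(0.80) = 0.2231.

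- M = 30%: Hd = -ln(0.70) = 0.3567. CIF = 0.2231/0.5798 × (1 - 0.80×0.70) = 0.3849 × 0.44 = 0.169. Factor 0.200/0.169 = 1.18.
- M = 60%: Hd = -ln(0.40) = 0.9163. CIF = 0.2231/1.1394 × (1 - 0.80×0.40) = 0.1958 × 0.68 = 0.133. Factor 0.200/0.133 = 1.50.

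A simulation of 1,000,000 patients gave the same values: crude incidence 0.169 and 0.133 against a 1-KM of 0.200 in both.

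**By follow-up time (constant hazards, K = 20% at 10 years).**

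| Time | M = 30% | M = 40% | M = 50% | M = 60% |
|---|---|---|---|---|
| 1 year | 1.02 | 1.03 | 1.03 | 1.05 |
| 3 years | 1.05 | 1.08 | 1.11 | 1.14 |
| 5 years | 1.09 | 1.13 | 1.18 | 1.24 |
| 10 years | 1.18 | 1.27 | 1.37 | 1.50 |

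**Event frequency matters little.** At 10 years, for M = 30% and 60%, K = 5% gives 1.19 and 1.52, and K = 30% gives 1.18 and 1.49.

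**Timing matters more.** At 10 years with M = 50% and K = 20%:

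| Event timing | Constant death hazard (b = 1) | Rising death hazard (b = 2) |
|---|---|---|
| Strongly early (a = 0.3) | 1.14 | 1.08 |
| Early (a = 0.5) | 1.22 | 1.12 |
| Steady (a = 1) | 1.37 | 1.22 |
| Late (a = 2) | 1.55 | 1.37 |

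With a = 0.3 and 0.5, 53% and 34% of the 10-year 1-KM has accrued by 1 year, against 11% with a = 1. Early clustering is plausible for pacemaker implantation and stroke, which are counted from the admission.

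At 5 years a rising death hazard (b = 2) brings the steady-onset factor down to about 1.03-1.07 for M = 30-60%.

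**Higher mortality.** A separate calculation with a constant event hazard of 2% per year and 10-year mortality of 50%, 70% and 85% gives 1-KM of 18.1% against CIF of 13.2%, 10.7% and 8.4%, that is factors of 1.37, 1.69 and 2.17.

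**Patients per arm of 531, at 10 years.**

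- Steady onset, 20% curve, M = 30-60%: reads as 531 × 0.200 = 106; true count 531 × 0.169 = 90 down to 531 × 0.133 = 71.
- Steady onset, 5% curve, M = 30-60%: reads as 531 × 0.05 = 27; true count 22 down to 17.
- Early clustering, 20% curve, M = 50%: reads as 106; true count 531 × 0.164 = 87 up to 531 × 0.186 = 99.

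**The case against.** The strongest reply is that this omission may never cause an error. The plan does not list which endpoints will be drawn, does not say that curves run to 10 years, and does not say that absolute incidence will be read from them. If only mortality and MACE are plotted, nothing is wrong. That stands, and it is why the point is conditional.

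The plan also has an incidence summary that does not use Kaplan-Meier. Numbers and percentages at fixed times, with largely registry-based follow-up, come close to the true cumulative incidence when follow-up is near complete. That stands too. It does not repair the curve, though, because the same paper would then carry two different 10-year figures.

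No planned inference is affected. Kaplan-Meier is for display only, and a Cox model that censors deaths gives a valid cause-specific hazard ratio. If mortality is similar on both valves, both curves are inflated by similar factors. This is correct, and it limits the severity.

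Finally, the size rests on assumptions, and the 5-year range of 1.09-1.24 holds for constant hazards only. With a rising death hazard the 5-year effect for steady-onset events is only a few percent. That is a fair limit: the case is strongest at 10 years and for events that occur late. The direction of the error does not depend on the assumptions.

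**Conclusion.** The concern holds, as a minor point. Applied to a non-fatal endpoint with deaths censored, the only display the plan names overstates absolute incidence. For steady-onset events with constant hazards and assumed 10-year mortality of 30-60%, the factor at 10 years is 1.18-1.50. At an assumed 50% mortality it runs from 1.08 for strongly early events to 1.55 for late ones. At 5 years, steady-onset events give about 1.03 to 1.24 depending on the shape of the death hazard, and at 1 year the effect is negligible (at most 1.05).

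These sizes rest on assumed mortality, frequency and timing. The overstatement itself follows whenever deaths precede the event. It is confined to the display of late secondary endpoints. The 1-year primary comparison, MACE at any time, mortality and cause-specific hazard ratios are untouched, and no changed conclusion between valves has been shown.

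**What to change.** Replace the display sentence in the Statistics section with text to this effect:

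> Kaplan-Meier curves will be used for all-cause mortality and MACE. Non-fatal secondary endpoints shown as time-to-event curves will be presented as Aalen-Johansen cumulative incidence curves with death as the competing event. Cox hazard ratios for these endpoints are cause-specific (deaths censored) and will be reported next to the mortality comparison.

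The between-valve comparison should stay with cause-specific Cox regression, read beside mortality. A cumulative incidence curve alone can make a valve with higher mortality look more durable, because fewer patients live long enough to have the event. Endpoints not drawn as curves need no change.

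The cost is a short change to one place in the SAP and standard software. No new data are needed, since mortality is already followed to 10 years. Cohort B is recruiting and the study is unblinded, so settling the estimator now avoids choosing it after results are seen. There are two limits. The new curves will be lower than, and not directly comparable with, Kaplan-Meier figures. The change also does not solve the unknown onset time between visits for echo-graded valve deterioration.
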